2 TRIAL OBJECTIVES AND ENDPOINTS

2.1 Objectives

Primary Objective

- To evaluate the effect of merotocin on increasing milk production in women with preterm delivery and with inadequate milk production

Secondary Objectives

- To evaluate the effect of merotocin on milk production after treatment discontinuation
- To evaluate the amount of mother's own milk (MoM) in the infant enteral nutritional intake and changes in infant body weight
- To evaluate any amount of merotocin from maternal plasma into the milk expressed by women with preterm delivery exposed to merotocin
- To characterize the safety profile of merotocin in women with preterm delivery and their infants

Exploratory Objectives

- To explore the relationship between merotocin exposure in maternal plasma and milk volume
- To evaluate composition of milk produced during treatment with merotocin in women with preterm delivery

Post-trial Objectives

- To explore post-trial feeding patterns and key parameters of neonatal intensive care unit (NICU) hospitalization of infants from women with preterm delivery and inadequate milk production
- To assess the post-trial long-term development of infants from women with preterm delivery and inadequate milk production

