Eligible maternal subjects will be randomly assigned in a 1:1 ratio to intra-nasal treatment with either merotocin (400 µg per dose, divided into 2 sprays with 1 spray in each nostril) or placebo. Randomization is stratified by gestational age group (<27 weeks and ≥27 weeks) and by site.

After instruction and guidance, treatment will be administered intra-nasally as 1 spray in each nostril approximately 5 to 10 minutes before each milk expression session. In this trial, treatment days start from the time of randomization, with Day 1 being the first 24 hours after randomization, Day 2 being 24 to 48 hours after randomization, and so on. The treatment period will include 14 such consecutive intervals of 24 hours from the time of randomization, corresponding to 14 treatment days (Days 1 to 14). Trial visits can be scheduled according to calendar days without considering 24-hour periods. Each administration of IMP and milk expression will be self-recorded

by maternal subjects. Maternal subjects should stop the administration of IMP as soon as having completed 14 days' treatment, rather than continue dosing until the Day 15/End-of-Treatment visit.

Trial visits after randomization include Day 3, Day 10, Day 15/End-of-Treatment and Day 18/Follow-up visits. At all of these visits, AEs and concomitant medications of maternal subjects will be collected and a review of the dosing (as applicable) and milk expression documentation will be performed.

Specifically, at Day 3 and Day 10 visits at the trial center, milk samples will be taken for the analysis of merotocin concentration in the milk and for the analysis of milk composition. Milk samples are taken only if the volume of production is, at the discretion of the investigator, adequate to meet the needs of the infant. In addition, for the analysis of merotocin concentration in the blood, 7 blood samples will be drawn for a minimum of 20 maternal subjects at Day 3 and Day 10 visits using an indwelling catheter at predefined time points from pre-dose until 1 hour after dosing. For the pre-dose sample of merotocin concentration, blood sampling should always be performed a minimum of 3 hours after the previous dose. Vital signs will also be measured at Day 3 and Day 10 visits.

Additional Day 15/End-of-Treatment visit procedures consist of a physical examination, vital signs and blood sampling (safety laboratory).

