3.2 Planned Number of Trial Centers and Subjects

Approximately 100 maternal subjects will be randomized at approximately 15 trial centers in the United States. It is anticipated that approximately 250 maternal subjects will be screened. See Section 9.1.

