3.6.6 Selection of the Trial Population

A high proportion of the mothers of premature infants experience challenges in establishing an adequate milk supply. Due to the prematurity of the infant and the infant's diminished ability to suckle, these mothers are often deprived of the natural stimulus for lactation and may be dependent upon a breast pump. Breast pump dependency means that the pump is the primary driver of milk removal and mammary gland stimulation even though the infant may be able to feed at the breast.³⁰ The stress of having a premature infant may further impede milk production. On the other hand, the potential benefits of MoM in preterm infants are well documented,^{2,31} which is likely to highly motivate mothers of preterm infants to express milk. For benefits to both mothers and infants, there are minimal ethical concerns about requiring a stringent milk expression schedule.

The trial population is women with infants at a high degree of prematurity. A gestational age range of 24 weeks + 0 days to 31 weeks + 6 days was originally chosen. However, by the amendment

(dated 06-04-2022), the window was expanded to 34 weeks + 2 days because many women who deliver infants at this gestational age are breast pump dependent and struggle to achieve an adequate milk supply. The upper limit of the gestational age is chosen to ensure the infants who are primarily breastfeeding at the time of enrollment would not be eligible. More breastfeeding may occur towards the end of the trial period among women who have delivered infants at the upper end of the gestational age range per eligibility criteria; however, that is not necessarily indicative of breast pump independence. Prematurity is one of several reasons for breast pump dependency; however, it is a focus of this early phase trial because of the high proportion of milk supply inadequacy experienced by women with premature birth.

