4 SELECTION OF TRIAL POPULATION

4.1 Trial Population

4.1.1 Inclusion Criteria

Inclusion criteria for entry into observation period:

Maternal subject:

1. Signed and dated informed consent for the maternal subject and parental consent for the infant prior to any trial activity.
2. Aged 18 to 44 years at the time of informed consent.
3. Delivered at the hospital system associated with the trial center.
4. Delivered a preterm singleton at a gestational age of 24 weeks + 0 days to 34 weeks + 2 days.
5. Attempted initial milk expression within 12 hours of delivery.
6. Attempted milk expression at least 3 times every 24 hours from 24 hours of delivery to the start of observation period (at least 3 times between 24 and 48 hours of delivery for subjects who enter the observation period within 48 hours of delivery).
7. Is willing to express milk at least 5 times every 24 hours during the observation period and 6 to 8 times every 24 hours during the treatment and post-treatment follow-up periods, including at least once during the night and with no more than 5 hours between milk expression sessions, during the trial (up to 23 days).
8. Is willing to refrain from sexual intercourse during the trial.

Inclusion criteria for randomization (in addition to the criteria above):

Maternal subject:

9. Attempted milk expression using the breast pump at least 5 times every 24 hours for the last 48 hours of the observation period, i.e., the 48 hours prior to the last pumping session before randomization.
10. Accurately recorded timing of milk expression after providing informed consent.
11. Produced <200 mL milk for the last 24 hours of the observation period (the 24-hour baseline interval), i.e., the 24 hours prior to the last pumping session before randomization.
12. Delivered 96 to 192 (+4) hours prior to randomization.

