7.2.7 Infant Body Weight

Infant body weight will be collected for the day of randomization (or last recorded measurements as available) and for all treatment days from Day 1 to Day 14 where data are available. Infant body weight may not be measured daily, so data can be missing for some treatment days.

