9.6.3 Secondary Endpoints

Secondary efficacy endpoints will be analyzed using the FAS and the PP analysis set, whereas secondary safety endpoints will be reported using the safety analysis set.

The time from randomization to the first occurrence of a daily volume of MoM ≥ 500 mL and ≥ 750 mL will be analyzed by fitting a discrete time survival model adjusted for gestational age group, as well as the baseline volume of MoM.

The proportion of maternal subjects producing at least 500 mL and 750 mL of MoM over Days 1 to 14 will be analyzed by repeated logistic regression adjusted for treatment day, treatment-by-day interaction and gestational age group.

The volume of MoM produced over Days 15 to 17 will be compared between treatment groups using a repeated measures ANCOVA model adjusting for the volume of MoM produced on Day 14.

Volume of MoM fed to the infant over Days 1 to 14 and volume of formula/donor milk fed to the infant over Days 1 to 14 will be analyzed and presented using an ANCOVA approach similar to the one used for the primary endpoint but gestational age will be adjusted for as a continuous covariate.

The proportion of subjects with quantifiable amount of merotocin in the milk will be summarized for the merotocin group.

Infant body weight will be summarized by treatment day, treatment group and gestational age measured in weeks, together with change from baseline values.

Maternal subject TEAEs will be summarized by treatment group, including separate summaries by intensity. All infant AEs will be summarized by treatment group, again including separate summaries by intensity. Further details are provided in Section 9.8.2.

Routine safety laboratory parameters of maternal subjects will be summarized by time point and treatment group, together with change from baseline values. For each laboratory parameter, a summary table will be prepared displaying the proportion of maternal subjects who have at least one markedly abnormal value. Markedly abnormal criteria for the safety laboratory parameters will

be specified in the SAP.

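### Infant weight change, a secondary endpoint, is only summarised by day, arm and gestational week, so the supplied plan gives no usable estimate of a treatment difference

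*Combined protocol and SAP*

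**What the plan says.** Section 2.2 lists infant weight change across the 14 treatment days among the secondary endpoints. The matching secondary objective in section 2.1 concerns the amount of mother's own milk "in the infant enteral nutritional intake and changes in infant body weight", so weight shares that objective with intake.

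The analysis in section 9.6.3 is a single sentence: "Infant body weight will be summarized by treatment day, treatment group and gestational age measured in weeks, together with change from baseline values". It names no model, adjusted difference, confidence interval or test.

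In the same section, the two endpoints on volumes fed to the infant get an ANCOVA like that for the primary endpoint, except that "gestational age will be adjusted for as a continuous covariate".

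On data, section 7.2.7 warns: "Infant body weight may not be measured daily, so data can be missing for some treatment days". Section 3.1.2 takes all infant data from hospital records, and section 9.6.1 rules out imputation for secondary endpoints.

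**The concern.** Weight and fed volumes sit under one objective and both depend on gestational age, yet the plan treats them differently. For fed volumes, gestational age enters as one continuous term and every infant contributes to a single arm comparison. For weight, infants are divided by completed week. That is much finer than the two groups (below 27 weeks, and 27 weeks or more) used for stratification in section 4.2.2 and for presentation by gestational age in section 9.6.1.

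A reader who wants to know whether weight gain differed between arms would have to compare many very small cell means by eye. The infants behind those means can also change from day to day, because weights are not taken daily and are not imputed. The stake is modest: an endpoint that the plan lists would be reported without the one summary that relates it to treatment.

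**Working it through.** **The plan's own figure.** There is none for infant weight: no SD, cell size or power is stated. Table 7 in section 9.1 concerns milk volume only, and its means and variances are not given. Nothing below depends on it.

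**Inputs.**
- Total: "Approximately 100 maternal subjects will be randomized at approximately 15 trial centers" (section 3.2).
- Allocation: "Eligible maternal subjects will be randomly assigned in a 1:1 ratio to intra-nasal treatment" (section 3.1.2), so 100/2 = 50 per arm.
- Infants: "Delivered a preterm singleton at a gestational age of 24 weeks + 0 days to 34 weeks + 2 days" (section 4.1.1), so one infant per mother.
- Drop-out: 30% over the trial (section 9.1), so 50 × 0.70 = 35 per arm by the end. Applying this maternal rate to infant weights is an assumption.

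**Number of cells.** Weeks 24 to 34 make 11 completed-week categories. Crossed with 2 arms and 14 days, that is 11 × 2 × 14 = 308 cells, or 22 on each day.

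**Average cell size on one day.**
- 50/11 = 4.5 infants.
- 35/11 = 3.2 infants.
- Days without a recorded weight lower both.

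**Spread around the average.** The documents give no gestational-age distribution. As an illustration, take births as uniform over the 73 eligible days:
- A full week expects 50 × 7/73 = 4.8 infants per arm. Week 34 covers only three days and expects 50 × 3/73 = 2.1.
- With 50 per arm, about 51% of cells hold four or fewer infants. With 35 per arm, about 78% do.
- With 50 per arm, about 35% of full-week cells hold six or more (binomial, 50 trials, probability 7/73).

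Before the amendment dated 06-04-2022 the range was narrower: "A gestational age range of 24 weeks + 0 days to 31 weeks + 6 days was originally chosen" (section 3.6.6). That is 8 categories. If all infants fell in that range, the averages would be 50/8 = 6.3 and 35/8 = 4.4, so infants enrolled earlier make weeks 24 to 31 fuller.

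**Precision of an arm difference, in SD units.** The 95% half-width is q × √(2/n), with n infants per arm.

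| Comparison | n per arm | q | Half-width |
|---|---|---|---|
| Within one gestational week | 4.5 | 2.365 (t, 7 df) | 2.365 × √(2/4.5) = 1.58 SD |
| All infants | 50 | 1.96 | 1.96 × √(2/50) = 0.39 SD |
| All infants, 30% drop-out | 35 | 1.96 | 1.96 × √(2/35) = 0.47 SD |

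At 3.2 per arm, even the normal quantile gives 1.96 × √(2/3.2) = 1.55 SD within a week; a t quantile would widen it.

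**Sensitivity to the equal-SD assumption.** Weight gain may vary more across 24 to 34 weeks than within one week, which would widen the all-infant interval. To cancel the advantage, the SD left after adjustment would have to be 1.58/0.39 = 4.1 times the within-week SD, or 1.58/0.47 = 3.4 times with 35 per arm.

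**The case against.** **The objective is descriptive.** In section 2.1 the milk-production objectives speak of the effect of merotocin, whereas the infant objective speaks of evaluating an amount and changes. Section 3.6.2 presents weight as a standard sign that the infant is growing as expected. This stands. A reader might infer that the objective cannot be answered from these tables, but the documents do not support that: a summary by arm with change from baseline can serve the objective as worded. What it cannot supply is a between-arm estimate.

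**The supplied text is an outline.** Section 9 defers detail to a SAP to be available before unblinding, and section 9.6.1 promises intervals and p-values for treatment differences where suitable. It would therefore be too strong to say that no comparison will ever be made. But the clause is conditional, does not mention infant weight and supplies no model, and nothing in the supplied text commits to a comparison.

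**The cell size is a mean.** It would be wrong to read 4.5 as a ceiling, since some cells will be clearly larger. Crossing the three factors is the natural reading of section 9.6.3 but still an inference. Separate one-way summaries would have larger cells, though still no comparison.

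**Nobody planned a contrast within one gestational week.** True. The 1.6 SD figure shows what the tables could support if used that way; it does not criticise a planned test.

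**A model does not remove selection.** This stands too. Hospital weights stop when an infant goes home, and discharge may be related to weight. A repeated measures model uses incomplete series better than raw means do, but a Day 14 difference would still rest on infants who remain in hospital.

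**Priority.** Proof of concept depends only on milk volume (section 9.6.2), and infant weight played no part in sizing the trial. That limits the weight of the point.

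**Conclusion.** The point holds as a cheap improvement of low to moderate priority. For this secondary endpoint the supplied plan specifies only a summary by day, arm and gestational week, and no between-arm estimate. The tables can describe growth but are a poor basis for judging a treatment difference: about 1.6 SD half-width within a gestational week, against 0.4 to 0.5 SD using all infants, roughly three to four times wider.

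The size rests on four assumptions: crossed factors, an even spread of gestational ages, the 30% drop-out carried over to infant weights, and the same SD in both comparisons. It is left in SD units because the documents give no SD for infant weight; a figure in grams would rest on an outside assumption. The absence of a specified comparison depends on none of these.

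**What to change.** In the SAP, before unblinding:

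1. Add a supportive repeated measures ANCOVA of infant weight change, with weight at randomisation, continuous gestational age, treatment, day and treatment-by-day. This follows the approach already planned for fed volumes. Randomisation weight, or the last recorded value, is already collected (sections 6.3 and 7.2.7).
2. Report the average difference over Days 1 to 14 and the Day 14 difference, each with a 95% CI, labelled as estimation and not as a powered test.
3. Show the number of infants contributing by day and arm, and state that late-day estimates rest on infants still in hospital.
4. Keep the descriptive tables, but in broad gestational bands such as the existing groups below 27 weeks and 27 weeks or more.

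The cost is SAP wording, one more model and one more comparison without multiplicity control. No new data are needed.

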9.6.4 Exploratory Endpoints

A population PK model will be developed describing merotocin concentrations in plasma and the relationship between merotocin exposure and milk volume will be explored. The analysis methods will be described in detail in a separate modelling analysis plan prepared by Ferring's Translational Medicine Department. This analysis plan will be available before breaking the blind of the trial and results of the analysis will be reported separately.

Milk composition variables will be summarized by time point and treatment group.

9.6.5 Post-trial Endpoints

Post-trial endpoints will be presented in summary tables.

9.7 Extent of Dosing and Treatment Compliance

Extent of actual dosing is defined as the number of intra-nasal trial treatment spray administrations and also as the number of days receiving trial treatment. Both variables will be summarized by treatment group.

Compliance is defined in terms of the number of milk expression attempts and the use of the nasal spray. For women attempting less than 6 milk expressions on a given day, their daily compliance is calculated as number of IMP administrations divided by 5 (the minimum number of milk expression attempts stated in the protocol). For women who perform 6-8 milk expression attempts, compliance is calculated as the number of IMP administrations divided by number of milk expressions. For women expressing milk more than 8 time per day, compliance is calculated as the number of IMP administrations divided by 8 (the maximum number of IMP administrations specified in the protocol). This will be done for both the overall treatment period and each treatment day. Compliance over Days 1 to 14 will be summarized by treatment group as the number of maternal subjects with at least 80% compliance.

Drug dosing will be evaluated by weighing each nasal spray bottle before dispensing and after return to the site taking into account the number of doses administered as reported by the maternal subject.

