The present trial is the first investigation in the target population of women with preterm labor and the first investigation with merotocin exposure beyond 45 hours. The proposed dosing regimen is 400 µg intra-nasal dose (divided into two sprays of 200 µg each) administered 6 to 8 times every 24 hours. The nasal spray can be used at consecutive sessions at least two hours apart for a maximum of 8 times every 24 hours. In the multiple ascending dose part of the phase 1 trial, the harmonic mean terminal half-life ($t_{1/2}$) with the 400 µg intra-nasal dose was 0.56 hours. With this $t_{1/2}$, merotocin concentrations are negligible at two hours after dosing (3.6 half-lives) and merotocin is considered to be eliminated at three hours after dosing (5 half-lives).

Regarding exposure of merotocin to the infants, transfer of merotocin from blood to breast milk was not observed in the phase 1 trial in healthy postpartum women specifically investigating this

risk, as the concentration of merotocin in the milk of all subjects was below the lower limit of quantification. Milk samples obtained in the present trial will also be evaluated for merotocin.

The blood sampling performed as part of the trial might be associated with mild discomfort, bruising, and a very rare risk of infection.

In conclusion, the evaluation of the benefits and risks indicates that participation in this trial is associated with a favorable benefit-risk ratio.

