5 TREATMENTS

5.1 Treatments Administered

5.1.1 Investigational Medicinal Products

The IMPs of the trial include merotocin nasal spray and placebo nasal spray.

Eligible maternal subjects will be randomly assigned in a 1:1 ratio to receive either merotocin nasal spray (400 µg per dose, divided into 2 sprays with 1 spray in each nostril) or placebo nasal spray. Maternal subjects will use their assigned nasal spray a maximum of 8 times every 24 hours (a maximum daily dose of 3200 µg) from the time of randomization for 14 treatment days (i.e., Days 1 to 14). Treatment is administered intra-nasally as 1 spray in each nostril approximately 5 to 10 minutes before a milk expression session. Each single spray constitutes half a dose (200 µg) and maternal subject must administer the spray in both nostrils to receive the 400 µg dose.

Subjects should aim to express milk 6 to 8 times every 24 hours including at least once during the night and with no more than 5 hours between milk expression sessions. As the IMPs will be administered only prior to milk expression, the exact daily dose of merotocin may vary for each maternal subject on each treatment day. [Table 1](#) presents the total daily dose of merotocin administered to maternal subjects based on milk expression frequency. The IMP should be administered prior to consecutive milk expression sessions at least 2 hours apart for a maximum of 8 times per treatment day. Subjects should follow instructions on how to use the nasal spray correctly and take precautions (e.g., washing hands after IMP administration but before milk expression) to avoid potential indirect transfer of IMP into milk.

Table 1 Total Daily Dose of Merotocin by Milk Expression Frequency

Milk Expression Frequency	Total Daily Dose of Merotocin (µg)
5 times per treatment day	2000
6 times per treatment day	2400
7 times per treatment day	2800
8 times per treatment day	3200
9 or more times per treatment day	3200

In this trial, treatment days start from the time of randomization, with Day 1 being the first 24 hours after randomization, Day 2 being 24 to 48 hours after randomization and so on. The treatment period will include 14 such consecutive intervals of 24 hours from the time of randomization, corresponding to 14 treatment days (Days 1 to 14).

Maternal subjects will be exposed to merotocin or placebo for 14 days, depending on randomization.

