6.4.1 All Treatment Days

Maternal subject-related activities:

- Lactation support is available to maternal subject
- Maternal subject administers the trial medication approximately 5 to 10 minutes prior to each milk expression session
- Maternal subject expresses milk 6 to 8 times every 24 hours including at least once during the night and with no more than 5 hours between sessions (Section 7.1.1)
- Maternal subject records the required details of dosing and milk expression on milk container labels in accordance with instructions provided in the lactation manual
- Maternal subject collects the milk into the supplied containers and labels and stores the containers appropriately
- Maternal subject will be contacted by the trial center staff to ensure compliance with the instructions for administration of the medication and recording of the milk expression

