9.3 Protocol Deviations

Protocol deviations will be rated as either minor or major. Protocol deviations impacting the primary endpoint will be rated as major. Maternal subjects will be excluded from the per protocol (PP) analysis set from the day where the first major protocol deviations occurred and onwards. Data will not be excluded from the PP analysis set in case of minor protocol deviations. Major protocol deviations include but are not limited to the following:

- For a given treatment day:
 - Less than 5 milk expression attempts
 - Less than 80% compliance with intra-nasal administration of assigned treatment prior to milk expression

The Ferring clinical team will perform a blinded review of protocol deviations before declaration of clean file and lock of database. If the blinded review identifies serious unforeseen deviations deemed to impact the primary endpoint and affect the conclusions of the trial, these will also be rated as major deviations. A comprehensive list of major protocol deviations will be detailed and documented in the clean file document prior to database release. Major protocol deviations will be tabulated by treatment day and treatment group.

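### Section 9.7 leaves the 2-hour spacing condition out of the compliance denominator, so two doses withheld because of it on one 6-, 7- or 8-session day become a major deviation

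*Combined protocol and SAP*

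**What the plan says.** **Compliance.** Section 9.7 uses three denominators: 5 on days with fewer than six expressions, 8 on days with more than eight, and the number of expressions in between: "For women who perform 6-8 milk expression attempts, compliance is calculated as the number of IMP administrations divided by number of milk expressions". It adds: "This will be done for both the overall treatment period and each treatment day".

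**Dosing, with a spacing condition.** Section 5.1.1: "The IMP should be administered prior to consecutive milk expression sessions at least 2 hours apart for a maximum of 8 times per treatment day". Section 1.3: "The nasal spray can be used at consecutive sessions at least two hours apart for a maximum of 8 times every 24 hours".

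**Dosing, without a spacing condition.** Section 6.4.1: "Maternal subject administers the trial medication approximately 5 to 10 minutes prior to each milk expression session". The trial-activities text in the Synopsis and in Section 3.1.2 says the same. The Synopsis (Medicinal Products) gives the regimen as 6 to 8 administrations per treatment day.

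**Sessions.** Section 7.1.1 and Table 5 ask for 6 to 8 sessions per 24 hours, at most 5 hours apart. No minimum gap is given, and each round of pumping is a session of its own.

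**Consequence.** For a given treatment day, Section 9.3 lists as a major deviation: "Less than 80% compliance with intra-nasal administration of assigned treatment prior to milk expression". It also states: "Maternal subjects will be excluded from the per protocol (PP) analysis set from the day where the first major protocol deviations occurred and onwards".

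**The concern.** Sections 5.1.1 and 1.3 place two limits on the spray: a minimum spacing and a daily cap. Section 9.7 respects the cap, because the denominator stops at 8 when no further dose is allowed. It does not respect the spacing. On a 6- to 8-session day, a session at which the spray was withheld because of the 2-hour condition counts as a missed dose.

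The treatment is also uneven. Two undosed sessions out of ten give 8/8 = 100%, while two undosed sessions out of eight give 6/8 = 75%.

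What is at stake is membership of the per-protocol set. That set supports the primary endpoint, its missing-data sensitivity analyses (Section 9.6.2) and the secondary efficacy endpoints (Section 9.6.3). Removal depends on behaviour after randomization and continues from the first flagged day.

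**Working it through.** **1. The plan's own figure.** Table 1 (Section 5.1.1) is the only stated figure that links doses to sessions. The formula 400 µg × min(sessions, 8) gives 2000, 2400, 2800, 3200 and 3200 µg for 5, 6, 7, 8 and 9 or more sessions, which matches every row. Table 1, like 9.7, therefore assumes a dose at every session up to 8.

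**2. Compliance under 9.7 with w doses withheld.** Formula for n = 6, 7 or 8 sessions: (n − w)/n.

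| Sessions | w = 0 | w = 1 | w = 2 |
|---|---|---|---|
| 6 | 100% | 5/6 = 83.3% | 4/6 = 66.7% |
| 7 | 100% | 6/7 = 85.7% | 5/7 = 71.4% |
| 8 | 100% | 7/8 = 87.5% | 6/8 = 75.0% |

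One withheld dose never falls below 80%. Two on the same day always do.

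**3. Can it happen within the 5-hour limit?** Yes, for all three counts.

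- 8 sessions at hours 0.2, 3, 4.5, 8, 12, 16, 17.5 and 21.5: two gaps of 1.5 h, none over 4 h, 6 doses.
- 7 sessions at hours 0.2, 4, 5.5, 9.5, 14, 18.5 and 20: two gaps of 1.5 h, none over 4.5 h, 5 doses.
- 6 sessions at hours 2.5, 4, 9, 14, 19 and 20.5: two gaps of 1.5 h, none over 5 h, 4 doses. This cannot repeat as an identical daily pattern, because two gaps under 2 h plus four of at most 5 h total less than 24 h.

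The dose counts are the same whether the 2 hours run from the previous session or the previous dose.

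**4. Against the daily range.** Six doses meet the 6 to 8 a day in the Synopsis. Five and four do not, and four doses (4 × 400 = 1600 µg) are below every row of Table 1.

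**5. Link from 9.3 to 9.7.** Section 9.3 does not cite 9.7. However, 9.7 holds the only compliance formula, applies it to each treatment day and uses the same 80% level.

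**6. The 14-day summary.** Thirteen days at 8/8 and one at 6/8 give 110/112 = 98%. If all days have 8 sessions, 11 days at 6/8 give 90/112 = 80.4% and 12 give 88/112 = 78.6%, so 12 of 14 days must be affected before a woman drops below 80%.

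**7. Frequency (assumed; not in the documents).** Let q be the share of days with two or more withheld doses, independent between days. The chance of at least one such day in 14 is 1 − (1 − q)^14. The share of woman-days lost under the onward rule is 1 minus the mean of (1 − q)^d over d = 1 to 14.

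| q | Women flagged | Woman-days lost |
|---|---|---|
| 1% | 13.1% | 7.2% |
| 2% | 24.6% | 13.8% |
| 5% | 51.2% | 30.5% |

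If clustering is habitual in some women, fewer women are ever flagged at the same q.

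**The case against.** **The regimen has a daily count too.** A per-protocol set may properly drop days with too few doses, and four or five doses are below the stated range. This stands: a reader might infer that all three cases remove women who met every dosing requirement, but the documents support that only for 6/8.

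**The 2-hour sentence may be an instruction to space sessions, and several sections simply call for a dose before each session.** The second part stands, and 9.7 fits that wording. But no minimum session gap is stated, and the wording of Section 1.3 limits the spray, not the pumping. Which instruction is intended is for the sponsor to settle.

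**Closely spaced dosing is rewarded.** A reader might infer this because dosing at every session scores 100%. It is not established: the 9.3 list is open-ended and completed at blinded review, and Section 8.1 says overdoses and medication errors are captured. That review is described as adding major deviations; nothing says that it may waive a listed one.

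**The wider harm is unproven.** This stands. Nothing in the documents ties clustered pumping to milk output, and the rates in step 7 are assumptions. A reader might also infer that the 14-day summary of women with at least 80% compliance is equally distorted; step 6 shows that it moves little unless clustering is frequent.

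**Conclusion.** The mismatch is real and narrow. Section 9.7 carries one of the two limits in Section 5.1.1 into the denominator and omits the other. Two doses withheld on the same 6-, 7- or 8-session day because of the 2-hour condition give 67%, 71% or 75% and, under 9.3, per-protocol removal from that day onwards. Earlier days stay in. The 8-session case is clearest, because those six doses satisfy both the spacing condition and the daily range.

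This rests on reading the 2-hour text as a condition on dosing and on 9.3 using the 9.7 formula. The dosing text in the Synopsis and Sections 1.3, 3.1.2, 5.1.1 and 6.4.1 is not consistent with itself or with 9.7 and must be reconciled.

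The effect is confined to the supportive per-protocol analyses and the daily compliance figures. The primary analysis and the proof-of-concept decision use the full analysis set (Section 9.6.2) and are unaffected. How often the problem occurs cannot be derived from the documents.

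**What to change.** First, the sponsor reconciles the dosing passages, stating whether the 2-hour text governs dosing and, if so, whether it runs from the previous session or the previous dose.

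Then, before unblinding, define the daily denominator in 9.7, and so the 80% rule in 9.3, as max(5, min(8, sessions at which a dose was due under the reconciled instruction)). Count in the numerator the doses given at those sessions. State in 9.3 that it uses this figure.

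This does not choose between the instructions. If a dose is due at every session up to 8, it gives the present 9.7 denominators unchanged. If the spacing condition governs, two withheld doses score 4/5 = 80%, 5/5 = 100% and 6/6 = 100% on 6-, 7- and 8-session days, none below 80%. A woman with eight doses due who takes six still scores 75%. The floor still flags days with three doses or fewer (3/5 = 60%), so under-dosed days are not admitted as fully compliant.

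The cost is a wording change and a slightly more complex derivation. Session times are already needed to assign milk to 24-hour treatment days, and dosing details go on the container labels (Section 6.4.1). Whether those include the clock time of each dose is left to the lactation manual and should be confirmed.
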